## 6. ENDPOINTS AND COVARIATES

### 6.1. Safety Endpoints

- Adverse events: All undesirable or unintended signs or symptoms that occurred after administration of this drug, regardless of causal relationship
- Adverse drug reactions: Adverse events assessed as causally related to this drug by the physician

- Serious adverse events or serious adverse drug reactions: Adverse events or adverse drug reactions assessed as serious by the physician

- Death after HSCT:

- Time to death after HSCT: Days and weeks from the date of first HSCT after the start of this drug to the date of death
- Event: Death (for any cause)
- Censoring: The patient is confirmed alive at the time of completion or discontinuation of the survey. The endpoint will be censored on the day when patient's survival was last confirmed.

Early death after HSCT is defined as the above event that occurred within 100 days after the first HSCT after the start of this drug. Early death is supposed to be absent if the patient died on 101 days or later, or was confirmed alive at the time of completion/discontinuation of the survey.

- Transplant-related death after HSCT (non-relapse death):

- Time to transplant-related death after HSCT: Days and weeks from the date of first HSCT after the start of this drug to the date of death.
- Event: Death due to non-tumor-related causes, resulting from worsening of the target disease of this drug
- Competing risks: Death due to tumor-related causes, resulting from worsening of the target disease of this drug
- Censoring: The patient is confirmed alive at the time of completion or discontinuation of the survey. The endpoint will be censored on the day when patient's survival was last confirmed.

Early transplant-related death after HSCT (non-relapse death) is defined as the above event that occurred within 100 days after the first HSCT after the start of this drug. Early death is supposed to be absent if the patient died on 101 days or later, or was confirmed alive at the time of completion/discontinuation of the survey.

- Transplant-unrelated death after HSCT (relapse death):

- Time to transplant-unrelated death after HSCT: Days and weeks from the date of first HSCT after the start of this drug to the date of death.
- Event: Death due to tumor-related causes, resulting from worsening of the target disease of this drug
- Competing risks: Death due to non-tumor-related causes, resulting from worsening of the target disease of this drug
- Censoring: The patient is confirmed alive at the time of completion or discontinuation of the survey. The endpoint will be censored on the day when patient's survival was last confirmed.

Early transplant-unrelated death after HSCT (relapse death) is defined as the above event that occurred within 100 days after the first HSCT after the start of this drug. Early death is supposed to

be absent if the patient died on 101 days or later, or was confirmed alive at the time of completion/discontinuation of the survey.

- Safety specification: Events included in safety specification will be specified separately.

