10.3. Causality Assessment

The investigator is required to assess and record the causal relationship. For all AEs, sufficient information should be obtained by the investigator to determine the causality of each AE. For AEs with a causal relationship to BESPONSA, follow-up by the investigator is required until the event and/or its sequelae resolve or stabilize at a level acceptable to the investigator, and Pfizer concurs with that assessment.

An investigator's causality assessment is the determination of whether there exists a reasonable possibility that BESPONSA caused or contributed to an AE. If the investigator's final determination of causality is "unknown" and s/he cannot determine whether BESPONSA caused the event, the safety event must be reported within 24 hours.

If the investigator cannot determine the etiology of the event but s/he determines that BESPONSA did not cause the event, this should be clearly documented on the CRF and the NIS AEM Report Form.

PFIZER CONFIDENTIAL

CT24-WI-JPN-GPSP01-RF09 8.0 Non-Interventional Study Protocol Template for Secondary Data Collection

Study 01-Nov-2023

Page 26 of 33

Inotuzumab

B1931024 NON-INTERVENTIONAL STUDY PROTOCOL

Amended 8, 12 December 2023

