## 7. HANDLING OF MISSING VALUES

The last observation date is defined as the latest full date among the following:

- Date of administration/discontinuation of this drug

- Date of onset/outcome of adverse event
- Date of assessment of hematologic response
- Date of MRD, laboratory tests, or ECG
- Date of ECOG PS assessment
- Date of hematopoietic stem cell transplant
- Start date of drug therapy or non-drug therapy for the target disease
- Date of survival assessment
- Date of last confirmed survival

If the date of death is missing or partial, it will be imputed based on the date of the last confirmed survival and the last observation date:

- If the date of death is missing, the date of the last confirmed survival will be used. If it is also missing, the last observation date will be used. If the day or month + day of the last confirmed survival is missing, the last observation date or the following date, whichever comes later, will be used.
  - If the day of the date of the last confirmed survival is missing: First day of the month and year when survival was last confirmed.
  - If the month + day of the date of the last confirmed survival are missing: January 1 of the year when survival was last confirmed.
- If the day or month + day of the date of death is missing, the date of the last confirmed survival, the last observation date, or the following date, whichever comes latest, will be used.
  - If the day is missing: First day of the month and year of death.
  - If the month and day are missing: January 1 of the year of death.

If the survival confirmation date is missing or partial, it will be imputed based on the last observation date:

- If the survival confirmation date is missing, the last observation date will be used.
- If the day or month + day of the survival confirmation date is missing, the last observation date or the following date, whichever comes later, will be used:
  - If the day is missing: First day of the month and year of the day of survival confirmation.
  - If the month and day are missing: January 1 of the year of the day of survival confirmation.

If for an adverse event, its seriousness, action made, or outcome is missing, it will be handled as "unknown" when summarizing data.

Cleaning-uncompleted data will be in principle handled as follows.

- Items with missing values: They will be handled as missing (or "unknown" for categorical variables) in both summary and listing.

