#### **8.2.3.1. Adverse drug reactions**

- **All adverse drug reactions**

The number and proportion of patients with adverse drug reactions will be tabulated by SOC and PT.

- **Details of adverse drug reactions**

ADRs categorized by each of the following factors will be summarized in terms of number and proportion of patients with ADRs by SOC and PT:

- Seriousness [serious, non-serious]
- Known/Unknown [known, unknown]
- Action taken (additional treatment for the AE) [performed, not performed]
- Action taken [discontinuation of treatment, temporary suspension or dose reduction, none]
- Outcome [fatal, not recovered, recovered with sequelae, recovering, resolved/recovered, unknown]
- CTCAE Grade (1) [1, 2, 3, 4, 5, unknown]
- CTCAE Grade (2) [ $< 3$ ,  $\geq 3$ , unknown]

Multiple occurrences of the same adverse drug reaction (with the same PT) in the same patient will be handled as follows in the summary:

- Seriousness: If both serious and non-serious events of the same AR occurred in the same patient, the patient will be counted as one with a serious reaction.
- Known/Unknown: If both known and unknown events of the same AR occurred, the patient will be counted as one with an unexpected reaction.
- Action taken: If multiple types of actions were taken for the same AR in the same patient, one action will be adopted in the order of priority of "discontinuation of treatment", "temporary suspension or dose reduction", and "none".
- Outcome: See below
- CTCAE Grade: If there are multiple grades, the highest grade will be used.

In the summary by outcome, multiple events of the same AR in the same patient will be handled as follows:

- Outcome: If multiple different outcomes were reported, one category of outcome will be adopted from "fatal", "not recovered", "unknown", "recovered with sequelae", "recovering", and "resolved/recovered" with priority in this order.

Each SOC and PT of serious ADRs will be summarized by outcome.

- **Safety specification**

Patients who experienced the events identified as the safety specification will be summarized in terms of n and proportion. Similar summary will also be performed by CTCAE Grade [ $< 3$ ,  $\geq 3$ , unknown].

In addition, events identified as the safety specification will be summarized in terms of number and proportion of patients with such events for each SOC and PT by actions taken and outcome thereof.

- **Timing of onset of adverse drug reactions**

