#### 8.2.3.2. Adverse events

- **Serious and non-serious adverse events**

The number (n) and proportion of patients with serious adverse events (SAEs) will be tabulated by SOC and PT. Similar summary will also be performed for non-serious adverse events (AEs), but a threshold will be set for the proportion as necessary, and summary will be performed only for events that are associated with a proportion at or above the threshold.

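### Events of unknown or missing causality are not ADRs under the SAP, so the ADR-only VOD/SOS and safety-specification analyses treat those patients as non-cases

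*SAP*

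**What the plan says.** **Causality.** SAP 6.1 makes a positive judgement the condition for an ADR: "Adverse drug reactions: Adverse events assessed as causally related to this drug by the physician". Protocol 10.3 asks the investigator to assess and record causality, but also provides for a final determination of unknown. If the investigator "cannot determine whether BESPONSA caused the event, the safety event must be reported within 24 hours". It treats separately the case where the investigator concludes that the drug did not cause the event.

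**Missing data.** The event-specific rule in SAP 7 is: "If for an adverse event, its seriousness, action made, or outcome is missing, it will be handled as 'unknown' when summarizing data". Causality is not among the three items. A general rule for data whose cleaning is not complete does reach it: "Items with missing values: They will be handled as missing (or 'unknown' for categorical variables) in both summary and listing". Items with inconsistent values are also set to missing.

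**Use.** The VOD/SOS part of SAP 8.2.3.1 is restricted to events reported as reactions. The subgroup analyses in SAP 8.2.3.4 for liver disorder, myelosuppression, infection and hemorrhage also use ADRs. Adverse events regardless of cause appear in SAP 8.2.3.2: "The number (n) and proportion of patients with serious adverse events (SAEs) will be tabulated by SOC and PT". A similar table is planned for non-serious events, with a threshold if needed. SAP 8.2.3 has the listings include all reported events. Protocol 10.2 has every VOD/SOS up to the end of follow-up reported as a serious adverse event, regardless of causality and severity.

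**The concern.** An event with undetermined causality has not been assessed as related, and no sentence in the SAP brings it into the ADR count. This matters most for VOD/SOS, the event on which the sample size rests. The survey collects VOD/SOS without regard to cause, then analyses only the events judged related.

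A patient with VOD/SOS of unknown causality is misclassified as well as uncounted. In the risk-ratio tables the patient stays in the denominator as a non-case. In the time-to-onset analysis the patient is handled as one without the reaction and is censored at discontinuation or last observation.

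The loss need not be even across subgroups. VOD/SOS is collected up to 52 weeks after the last transplant, and SAP 6.4 names transplant and conditioning agents among the potential risk factors. Attribution to the drug is plausibly harder in that setting, so unknown causality could cluster in the groups being compared. The documents contain no data on this.

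**Working it through.** **1. Where each kind of event goes, on the SAP's wording**

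| Causality | Seriousness | Adverse event tables (8.2.3.2) | ADR tables and analyses (8.2.3.1, 8.2.3.4) | Listings |
|---|---|---|---|---|
| Unknown or missing | Serious | Yes | No | Yes |
| Unknown or missing | Non-serious | Yes, unless below a threshold | No | Yes |
| Unknown or missing | Unknown | No | No | Yes |
| Related | Unknown | No | Yes, except the seriousness split | Yes |
| Unrelated | Unknown | No | No | Yes |

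Under Protocol 10.2 a VOD/SOS event of unknown causality should sit in the first row: in the serious event table and the listings, but in none of the VOD/SOS analyses.

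**2. The plan's own figure.** Protocol 8.10.2 gives 80.4% power for 176 patients (88 per group), incidences of 18.5% and 6.2%, and a two-sided chi-square test at 0.1. With the pooled-variance normal approximation,

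z = [|p1 − p2|·√n − 1.645·√(2·p̄·(1 − p̄))] / √[p1(1 − p1) + p2(1 − p2)]

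= [0.123 × 9.381 − 1.645 × 0.4653] / 0.4571 = 0.850, which gives 80.2%. Less rounded rates of 18.45% and 6.15% give 80.4%. The stated power reproduces.

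**3. Effect on the VOD/SOS proportion (assumed loss).** Expected patients: 0.123 × 176 = 21.6, taken as 22; 22/176 = 12.5%. The loss of 2 to 4 patients is an assumption.
- Loss of 2: 20/176 = 11.4%, a relative loss of 2/22 = 9%.
- Loss of 4: 18/176 = 10.2%, a relative loss of 4/22 = 18%.

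**4. Effect on the risk-factor comparison (same kind of assumption).** Let a share f of VOD/SOS events have unknown causality.
- Equal loss in both risk groups: the relative risk is unchanged, and power falls from 80.2% to 75.9% at f = 10% and to 70.9% at f = 20%.
- Loss in the high-risk group only: the relative risk falls from 0.185/0.062 = 2.98 to 0.1665/0.062 = 2.69 at 10% and to 0.148/0.062 = 2.39 at 20%.
- Loss in the low-risk group only: it rises, at 20% to 0.185/0.0496 = 3.73.

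The proportion can only be understated. The risk ratio can move either way.

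**The case against.** A reader might infer that doubtful events disappear from the safety summaries altogether. The documents do not support that. The tables in SAP 8.2.3.2 do not depend on causality, the overall ADR table does not depend on seriousness, and the listings include everything, with a dedicated listing for VOD/SOS adverse events. Only three groups miss every event table: events with both attributes unknown, unrelated events of unknown seriousness, and non-serious events of unknown causality below any threshold.

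It would also be wrong to say that SAP 7 has no rule for missing causality. Its general rule applies, but the result, unknown, still does not satisfy SAP 6.1.

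The strongest counter-argument is that Protocol 10.3 sets a reporting duty and does not define an ADR for analysis. Its causality standard is already broad, a reasonable possibility of a contribution, and investigators must record an assessment, so unknowns may be few. The form's response options are not shown. The data-handling guidance cited in SAP 5.1 is not included and could contain a rule. All of this limits the likely size. It does not remove the gap: the SAP cites that guidance for analysis-set criteria, and neither SAP 6.1 nor SAP 7 refers to it for causality.

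**Conclusion.** The point holds for the ADR-based analyses only. Read literally, the SAP counts a patient whose event has unknown or missing causality as a non-case in the VOD/SOS occurrence, timing and risk-factor analyses and in the safety-specification subgroups. For VOD/SOS this sits poorly with a protocol that collects the event regardless of cause.

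The size is not known. The fall from 12.5% to between 11.4% and 10.2%, and the power and relative-risk figures, rest on assumed losses with no source in the documents. They also assume that no classification rule exists elsewhere.

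The seriousness gap is secondary. SAP 7 promises an unknown category, but the ADR seriousness split has two levels and SAP 8.2.3.2 plans two tables. Outcome and CTCAE grade do have an unknown level. This is a table-layout omission, and it hardly touches VOD/SOS, which must be reported as serious.

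**What to change.** 1. In SAP 6.1 and 7, define an ADR as an adverse event for which the physician did not rule out a causal relationship, with unknown or missing causality counted as an ADR. Footnote the number of events classified this way.
2. In SAP 8.2.3.1, add an all-causality sensitivity analysis of VOD/SOS occurrence and risk factors.
3. As a secondary change, add an unknown seriousness level to the tables in SAP 8.2.3.1 and 8.2.3.2, so that SAP 7's own rule takes effect. Do not recode missing seriousness as serious. That would contradict SAP 7 and the SAP 6.1 definition of serious events: "Adverse events or adverse drug reactions assessed as serious by the physician".

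The cost is SAP wording, one derivation rule, a few table rows and one repeated analysis on data already collected. The downside is slightly higher ADR counts, which the footnote lets a reader undo.

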#### 8.2.3.3. Other endpoints

- **Death after HSCT**

To investigate early deaths after HSCT (see Section 6.1 for definition), the following kinds of patient data will be summarized as per Section 8.1.2. The denominator of a proportion is the number of patients included in the 1-step higher itemization level.

- Patients in the SAS who underwent HSCT after the start of this drug and have finished the survey (Patients who are recorded as discontinued in the "Record of continued/discontinued survey [treatment period]" in the case report form or patients for whom "Record of continued/discontinued survey [follow-up period]" in case report form is filled in. The latter means the survey is discontinued and completed for the patient.)
  - Death after HSCT
    - ◊ Death within 100 days post-HSCT
    - ◊ Death after > 100 days post-HSCT
    - ◊ Transplant-related death (non-relapse death)
      - Death within 100 days post-HSCT
      - Death after > 100 days post-HSCT
    - ◊ Transplant-unrelated death (relapse death)
      - Death within 100 days post-HSCT
      - Death after > 100 days post-HSCT

- Survival confirmed at the time of discontinuation of the survey
- **Mortality after HSCT**

Time to death after HSCT, time to transplant-related death after HSCT, and time to transplant-unrelated death after HSCT (see Section 6.1 for definitions) will be analyzed as per Section 8.1.4 (Although the time to death after HSCT does not have any competing risk, the same analysis with competing risks will be performed for the variable). Those who included in the analysis are patients in the SAS who underwent HSCT after the start of this drug and finished the survey (Patients who are recorded as discontinued in the "Record of continued/discontinued survey [treatment period]" in the case report form or patients for whom "Record of continued/discontinued survey [follow-up period]" in case report form is filled in. The latter means the survey is discontinued and completed for the patient.). The cumulative incidence will be estimated at Week 4, Week 8, Week 12, Day 100, Week 24, Week 36, Week 48, Week 52, Week 78, and Week 104.

- **Exploration of factors associated with early death after HSCT (subgroup analyses)**

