Patients with early death after HSCT will be summarized in terms of n and proportion by each of the following factors selected from those specified in Section 5.4. In addition, risk ratios for the proportion of patients who died for different subgroups will be determined as per Section 8.1.3 and presented graphically. If, however, there is a category with less than 10 patients and after reconsideration it is considered difficult to determine the risk ratio for the category, it will not be determined for the relevant category. To investigate correlation between factors and death, statistical tests specified in Section 8.1.3 will be performed. Similar analyses will also be performed for early transplant-related death after HSCT (non-relapse death).

- Age [< 15 years, > 15 to < 65 years, ≥ 65 years]
- Age [< 18 years, ≥ 18 to < 55 years, ≥ 55 years]
- Age [< 15 years, ≥ 15 to < 40 years, ≥ 40 years]
- Disease name
- Chromosome karyotype [normal, t (4;11)]
- Chromosome karyotype [Philadelphia chromosome positive, negative] \* Philadelphia chromosome is considered positive if the chromosome karyotype is t(9;22).
- Hepatic impairment
- Medical history (past) - VOD/SOS
- Medical history (past) - GVHD
- Medical history (past) - Hepatitis or hepatic disease
- Medical history (present) - VOD/SOS
- Medical history (present) - GVHD
- Medical history (present) - Hepatitis or hepatic disease
- ECOG PS before the start of this drug [0, 1, ≥ 2, not performed]
- Hemoglobin level immediately before the start of this drug
- Platelet count immediately before the start of this drug
- Peripheral blast count immediately before the start of this drug

- Myeloblast count immediately before the start of this drug
- Salvage line of the induction treatment with this drug
- HSCT before the start of this drug
- Type of the first HSCT after the start of this drug
- Donor of the first HSCT after the start of this drug
- Conditioning with alkylating agent for the first HSCT after the start of this drug
- Conditioning with busulfan for the first HSCT after the start of this drug
- ECOG PS before conditioning for the first HSCT after the start of this drug [0, 1,  $\geq 2$ , not performed]
- Hemoglobin level before conditioning for the first HSCT after the start of this drug
- Platelet count before conditioning for the first HSCT after the start of this drug
- Peripheral blast count before conditioning for the first HSCT after the start of this drug

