- Myeloblast count before conditioning for the first HSCT after the start of this drug
- Time from the date of final dose of this drug to the date of the first HSCT after the start of this drug
- Treatment cycles [1 cycle, 2 cycles, 3 cycles, 4 cycles, 5 cycles, 6 cycles,  $> 6$  cycles]
- Treatment cycles [ $\leq 3$  cycles,  $\geq 4$  cycles]
- Best overall response
- MRD
- Best overall response and MRD
- Adverse drug reactions that occurred during the treatment period - liver disorder as a safety specification

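### Patients who leave the survey alive before Day 100 after HSCT are coded as free of early death, so early-death proportions by factor read low and risk ratios shift if early loss differs by factor

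*SAP*

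**What the plan says.** SAP 6.1 defines early death as death within 100 days of the first HSCT after the start of the drug, and sets it to "absent if the patient died on 101 days or later, or was confirmed alive at the time of completion/discontinuation of the survey". The same sentence is repeated for early transplant-related and early transplant-unrelated death. For the time-to-event form of each endpoint, the same section says: "The endpoint will be censored on the day when patient's survival was last confirmed".

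SAP 8.2.3.3 uses early death in two places.

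- **Death after HSCT table.** The population is HSCT patients who finished the survey, which expressly includes those recorded as discontinued. "The denominator of a proportion is the number of patients included in the 1-step higher itemization level". Patients alive have one row, "Survival confirmed at the time of discontinuation of the survey", which is not split at Day 100.
- **Factor exploration.** Early death is summarised by n and proportion over 36 listed factors, and "risk ratios for the proportion of patients who died for different subgroups will be determined as per Section 8.1.3", with the tests of that section. The same is done for early transplant-related death.

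Between these two, 8.2.3.3 also plans cumulative incidence at a set of times that includes Day 100, for all HSCT patients together.

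Protocol 8.7 plans observation until 52 weeks after HSCT. Protocol 8.8.9 lists no further visit, transfer and other among the reasons for leaving the survey.

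**The concern.** Completing the survey alive is sound evidence of surviving 100 days, because planned follow-up runs well past that point. Discontinuing alive is not. A patient last seen on Day 20 has unknown Day-100 status but stays in the denominator as a non-event. The coded proportion therefore falls below the true risk by the deaths that occur, unseen, between leaving and Day 100.

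Risk factors for early death in HSCT patients are a named objective (Protocol 7.2, SAP 2.2), and the factor exploration is the analysis that addresses it. If patients in one category leave sooner than those in another, for example because of more transfers, the risk ratio moves for a reason unrelated to mortality. No planned output shows early loss by factor, so a reader could not detect this. The crude figures can also disagree with the Day-100 cumulative incidence in the same report.

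**Working it through.** **What the documents supply.** They give no early-death rate, no rate of loss before Day 100 and no number of HSCT patients. The one design calculation, 80.4% power for VOD/SOS, does not bear on this endpoint. The only allowance for loss is in Protocol 8.10.1: 200 enrolled for 176 analysed, so 24/200 = 12%, covering all exclusions and dropouts. Death and loss rates below are therefore assumptions, shown over a range.

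**Formula.** Assume constant hazards over 100 days and loss independent of death. Let *p* be the true Day-100 risk and *L* the probability of leaving by Day 100 if death did not intervene.

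- *d* = −ln(1 − *p*)/100 and *l* = −ln(1 − *L*)/100
- Coded proportion = *d*/(*d* + *l*) × [1 − exp(−100(*d* + *l*))]
- Proportion if early leavers are dropped = coded / [coded + (1 − *p*)(1 − *L*)]

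Example, *p* = 25% and *L* = 12%: *d* = 0.002877, *l* = 0.001278, coded = 0.6923 × (1 − 0.75 × 0.88) = 0.6923 × 0.34 = 23.5%.

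**Proportions.** The transplant-related column assumes a true 15% with 10% relapse death, so it is 15/25 of the all-cause coded value.

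| Lost by Day 100 | All-cause, true 25%, as coded | Transplant-related, true 15%, as coded | All-cause if early leavers are dropped |
|---|---|---|---|
| 5% | 24.4% | 14.6% | 25.5% |
| 12% | 23.5% | 14.1% | 26.3% |
| 20% | 22.5% | 13.5% | 27.3% |

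If 12% loss is instead spread evenly over the 52 weeks after HSCT, loss by Day 100 is 1 − 0.88^(100/364) = 3.5%, and 25% reads 24.6%. In simulation (400,000 patients per setting), the censored all-cause estimate was 24.9% to 25.0% at all three loss rates.

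**Risk ratios, true 30% against 15% (RR 2.0).**

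| Loss, high-risk vs low-risk group | Coded proportions | RR |
|---|---|---|
| 12% vs 12% | 28.3% / 14.1% | 2.00 |
| 20% vs 20% | 27.1% / 13.5% | 2.01 |
| 12% vs 5% | 28.3% / 14.6% | 1.93 |
| 5% vs 12% | 29.3% / 14.1% | 2.08 |
| 20% vs 5% | 27.1% / 14.6% | 1.85 |
| 5% vs 20% | 29.3% / 13.5% | 2.17 |

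With no true difference (25% in both groups), 20% against 5% loss gives 0.92 or 1.08.

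**Death after HSCT table.** Suppose 25% die by Day 100 and 50% by Day 364, with 12% early loss and none later. Early deaths read 23.54%. Those still followed at Day 100 are 0.75 × 0.88 = 66%, of whom one third die later, giving 22%. All deaths read 45.54% instead of 50%. Because the nested percentage divides by all deaths, the share within 100 days prints as 23.54/45.54 = 51.7% against a true 50%. So the count of early deaths and the overall death percentage read low, while the nested percentage can read slightly high.

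**Whether another planned output covers this by factor.**

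- The Day-100 cumulative incidence (8.2.3.3) censors early leavers, but for the whole group only.
- The Cox analyses of OS by factor in HSCT patients (8.2.4.5) censor, but are not Day-100 estimates. Their factor list in 5.4 shares 15 of the 36 early-death factors and omits donor, conditioning and hepatic factors.
- The follow-up table (8.2.1) counts patients with under 12 or 13 weeks after HSCT, but not by factor.

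**The case against.** The strongest case is that the effect is too small to matter. On the even-spread reading of the 12% allowance the shift is 0.4 points, and the 20% against 5% contrast rests on no figure in the documents. Sampling error is far larger: the 95% interval for a risk ratio of 2.0 is 1.11 to 3.61 with 88 per group, and 0.83 to 4.81 with an assumed 40 per group. Censoring also costs variance. In simulation with 40 patients, a true 30% and 20% loss, root mean squared error is 7.6 points crude against 7.7 censored. The censored estimate wins clearly only in larger groups with heavy loss (5.6 against 5.2 points at 88 patients, same rates). P-values are descriptive (SAP 4.1), missing information is a declared limitation (Protocol 8.14), transferred patients may be followed through the receiving hospital, and the rule names only patients confirmed alive, so not every leaver need be affected.

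All of this stands as a limit on size. It does not remove the defect. The error in the proportions has a known direction and does not shrink with more patients. Unequal loss cannot be seen in any planned table. In an exploratory survey the descriptive estimate is the result itself. One further caution also stands: if loss relates to prognosis, censoring is biased too. At 12% loss and a true 25%, leavers with twice the death hazard after leaving give 22.4% crude and 23.8% censored; with half the hazard, 24.2% and 25.7%.

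**Conclusion.** The concern holds. The coding rule makes every crude early-death proportion by factor a lower bound, not labelled as one, whenever patients leave alive before Day 100, and it conflicts with the censoring rule in the same section. With no early loss there is no bias, and with equal loss the risk ratios are almost unchanged. With unequal loss they move in either direction. Under the assumptions above the shift is about 0.4 to 2.5 points on a true 25%, and about 0.07 to 0.17 on a true risk ratio of 2.0. The actual size cannot be known from the documents. It affects the description and screening of factors, not a decision rule, so it should be corrected but does not undermine the survey as a whole.

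**What to change.** - For each factor in the 8.2.3.3 exploration, report Day-100 cumulative incidence by the Section 8.1.4 method, censoring at last confirmed survival. For transplant-related death, treat relapse death as the competing event.
- Where numbers allow, add a hazard ratio over the first 100 days, subject to the SAP's existing rule for categories with fewer than 10 patients. Say whether it is cause-specific or subdistribution for transplant-related death, since 8.1.4 does not.
- State the assumption that loss is independent of death.
- If the crude proportions by factor are kept, label them lower bounds and show, by factor, the number alive with under 100 days of confirmed follow-up. If that number is nil, the table itself shows there is no problem.
- In the Death after HSCT table, split the row for patients alive at Day 100. Do not label the nested percentage within 100 days a lower bound.
- Do not simply drop early leavers: that overstates the risk (26.3% for a true 25% at 12% loss).

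The cost is SAP wording and modest programming, because the estimation methods are already specified. Intervals widen slightly: the simulated standard error for a true 30% with 40 patients and 20% loss is 7.7 points against 7.0 crude.
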